##### 4.5.1 Demographic variables

Demographic variables include:

- Age (years) populated by the IWRS system,

CCI

CONFIDENTIAL

Project Document Version No. 3.0

Project Document Effective Date: 04-Oct-2017

Page 25 of 79

- Age in classes: 4-5 and 6-11, split as 6-8 and 9-11 years old (respectively 4 to 6 (excluded), 6 to 12 (excluded), 6 to 9 (excluded) and 9 to 12 (excluded)),
- Sex,
- Race/Ethnic origin as collected in the eCRF (Caucasian, Black, Hispanic, Asian, Other),
- Race using the following mapping: White (e-CRF value = “Caucasian”), Black or African American (e-CRF value = “Black”), Asian (e-CRF value = “Asian”), Other (e-CRF value = “Hispanic” or “other”)

When the date of birth is partial (only year available or year and month), the earliest possible date will be considered (e.g. first of January or first day of the month). Comparability at Baseline will be assessed using statistical tests on age, age by category and sex.

#### 4.5.2 Baseline Characteristics

Baseline characteristics include:

- Body weight (kg) [weight (in kg) = weight (in lb.) / 2.204623]
- Height (cm) [height (in cm) = 2.54 × height (in inches)]
- Body surface area (m^2):  $0.007184 \times (\text{height}(\text{cm})^{0.725}) \times (\text{weight}(\text{kg})^{0.425})$ ,
- Body mass index (kg/m^2): weight / (height(m)×height(m)),
- Spirometry: FEV1 value (L), FEV1 Percent Predicted (%), (also to be reported by age class 4-5, 6-8 and 9-11 years)
- Peak expiratory Flow (PEF): PEF value (L/min), PEF percent predicted (%), (also to be reported by age class 4-5, 6-8 and 9-11 years),
- Immunological markers: peanut-specific IgE (kU/L), peanut-specific IgG4 (mg/L),
- Skin Prick Test (SPT): Mean and longest wheal diameter for undiluted Peanut extract (mm) (Longest wheal diameter will be also reported for the following age classes: 4-5 and 6-11)
- Medical history (see [Section 4.5.3](#))
- Parental atopic medical history (see [Section 4.5.4](#))
- Disease history (see [Section 4.5.5](#))
- Screening ED subgroup and screening ED randomization stratum
- Filaggrin mutation group: subjects with mutation in the filaggrin gene (Heterozygous / Homozygous) versus wild type subjects.
  - A filaggrin mutation is defined as a positive result (“heterozygous”, “homozygous” or “indeterminate”) on at least one of the following gene loci: R501X, 2282Del4, R2447X, S3247X, 3702delG.
    - Heterozygous is defined as at least 1 mutation in a single gene locus, or more than 1 mutation in different gene loci (at least one gene with “heterozygous” or “indeterminate” result, no gene with “homozygous” result)
    - Homozygous is defined as 2 identical mutations at the same locus (at least one gene with “homozygous” result)

- r Wild type subjects will be identified as “Negative detection” (no positive results on all five genes)
- Comparability at Baseline will be assessed using statistical tests on Body mass index, Immunological markers, skin Prick Test, filaggrin mutation group, Screening ED subgroup and screening ED randomization stratum.

#### 4.5.3 Medical history

Medical history covers the collections of information on past or current conditions (apart from peanut allergy) along with start and end dates including:

- Any allergy other than peanut
  - PT terms which contains “ALLERG” (excluding LLT “Peanut allergy”) and PT terms which contains “HYPERSENSITIVITY” (excluding LLT “Peanut allergy”)
- Other atopic conditions (Exhaustiveness of the list of terms specified below will be reviewed during the data review meeting):
  - r Asthma
    - SMQ Asthma/bronchospasm MedDRA Version 19.1 from narrow terms: List of PT terms: Asthma, asthma exercise induced, asthma late onset, asthmatic crisis, bronchospasm, bronchial hyperreactivity, infantile asthma, status asthmaticus, wheezing
  - r Eczema/Atopic Dermatitis
    - List of PT terms: dermatitis atopic, dermatitis Allergic, Eczema, Application site eczema, Eczematous dermatitis, dermatitis contact.
  - r Allergic Rhinitis
    - List of PT terms: Rhinitis Allergic, seasonal allergy, Rhinitis perennial, conjunctivitis allergic
- Past or current medical conditions:
  - r Cardiovascular, respiratory (including asthma), gastrointestinal, renal, hepatic, neurological, endocrine, lymphatic, hematologic, immunologic, dermatological (including atopy), psychiatric, developmental, and genitourinary disorders, drug and surgical history and any other diseases or disorders.

They will be coded using the latest available version of the Medical Dictionary for Regulatory Activities (MedDRA) dictionary and will be reported by SOC and PT. The number and percentage of subjects with at least one medical history term will also be provided

Comparability at Baseline will be assessed using statistical tests on subjects with/without asthma, with/without eczema/atopic dermatitis, with/without allergic rhinitis and with/without any other allergy than peanut.

#### 4.5.4 Parental atopic medical history

Parental (father only, mother only, or both parents) atopic medical history covers: asthma, seasonal allergies, perennial allergies, food allergies, eczema/atopic dermatitis and other allergic diseases. The number and percentages of subjects with at least one parental atopic medical history will also be provided.

In case a subject's parent is not the biological parent, no parental medical history is collected about this parent.

#### 4.5.5 Disease history

Disease history covers the collection of information about the peanut allergy of the subject and will be reported using the following characteristics:

- Age at peanut allergy diagnosis (in years, calculated as Date of diagnosis – Date of birth divided by 365.25),
- Time since peanut allergy diagnosis (in years, calculated as Date of Informed consent - Date of diagnosis divided by 365.25),
- Category of the physician who made the diagnosis,
- Main reason having led to the diagnosis (reaction after ingestion, parental/sibling history of atopy, other risk factors)
- Diagnosis criteria (Allergic reaction(s) following peanut consumption, Positive SPT to peanut, Positive titer of peanut-sIgE, Positive Double-Blind Placebo-Controlled FC to peanut, Positive Single-Blind Placebo-Controlled FC to peanut, Positive Open FC to peanut)
- Most recent results of peanut allergy diagnostic tests performed,
- Description of allergic reactions:
  - ⌞ Number of allergic reactions after ingestion of peanut,
  - ⌞ Number of allergic reactions after ingestion of peanut in the previous 12 months,
  - ⌞ Time since last reaction after ingestion of peanut (in years, calculated as Date of Informed consent - Date of last reaction divided by 365.25). When the date of last reaction is partial (only year available or year and month), the latest possible date will be assumed (e.g. 31st of December or last day of the month).
  - ⌞ Allergic reaction after ingestion of peanut after the age of 2 years old

When the date of diagnosis is partial (only year available or year and month), the latest date between the date of birth and the earliest possible date of diagnosis (e.g. first of January or first day of the month) will be considered.

#### 4.6 Previous and concomitant medications

All medications taken before the study entry, at study entry and during the study will be recorded and coded using the latest available version of the World Health Organization (WHO) Drug Dictionary.

Medications will be classified either as “Prior only” (P), “Both Prior and Concomitant” (PC) or “Concomitant only” (C).

This classification will be made by comparing the study medication start and stop dates with the date of first application of study medication (or V4 date if date of first patch application is not completed).

Medications starting after the completion/withdrawal date will be listed but will not be classified or summarized.

“Prior only” (P) medications will be:

- Medications that were taken within 6 months prior to the date of first application of study medication and that stopped before the first application of study medication,
- Medications with partial start/stop date where there is clear evidence to suggest that the medication stopped within 6 months prior to the date of first dose of study medication.

“Both prior and concomitant” (PC) medications will be:

- Medications starting before the date of first application of study medication and stops on or after the date of first application of study medication,
- Medications with partial start/stop date where there is clear evidence to suggest that the medication started prior to the date of first dose of study medication (no evidence for the stop date).

“Concomitant only” (C) medications will be:

- Medications with a start date on or after the date of first dose of study medication,
- Medications with partial start/stop date where there is clear evidence to suggest that the medication started after the date of the first dose of study medication,
- Medications with partial or complete stop date where there is clear evidence to suggest that the medication stopped after the date of the first dose of study medication (no evidence for the start date or V4 date if date of first application is not completed),
- All other medications with partial start/stop date where there is no clear evidence to suggest that the medication started or stopped before or after the date of the first dose of study medication.

For prior and/or concomitant medications, number and percent of subjects overall and per ATC class (level 3) and preferred drug name will be calculated. The following summaries will be presented:

- Prior medications (other than the ones taken during the food challenge at Baseline), prior only medications (P) will be taken into account;
- Concomitant medications (other than the ones taken for the food challenge at M12 and the ones taken for voluntary or accidental consumption of peanut), both prior and concomitant (PC) and concomitant (C) medications will be taken into account;
- Medications taken for food challenges, by time point;
- Concomitant medications taken due to accidental/voluntary consumption of peanut.

Number of antihistamines and number of epinephrine intakes during food challenges will also be tabulated separately (for the Peanut and Placebo days of DBPCFC separately). Non-drug therapies and surgical procedures are collected and will be coded using the latest available version of the MedDRA Dictionary. They will be also presented by SOC and preferred term and listed.

Prior and concomitant medications as well as Non-drug therapies and surgical procedures will be summarized by treatment group and overall for the safety population.

All prior and concomitant medications, non-drug therapies and surgical procedures will be listed.

#### 4.7 Study duration, treatment exposure and compliance

The overall study duration for each subject will be approximately 61 weeks (6-week screening period, 12-month treatment period and 2-week follow-up period).

Study duration (days) will be calculated as:

- Last study visit date - Date of informed consent +1.

During the 12-month blinded treatment period, the Viaskin® patch must be applied on the skin for 24 hours every day, except during the initiation of treatment, where the duration of application of the Viaskin® patch will be progressively increased as follows:

- During the first week (from Day 1 through Day 7), the patches will be applied for 6 hours every day,
- During the second week (from Day 8 through Day 14), the patches will be applied for 12 hours every day,
- From the third week onwards (Day 15), the patches will be applied for the entire 24 hours daily.

Treatment exposure will be based on:

- The exposure duration (in days, regardless of treatment interruption), calculated for the following periods:
  - ⌞ Over the whole study period as: Date of last patch application – Date of first patch application +1,
  - ⌞ At each study visit (Day 8, Month 1, 3, 6, 9, 12) as: Date of last patch application before the visit – Date of first patch application at the preceding visit+1.
- The total dose of peanut protein (in mg) received via the patch during the study, calculated for the following periods:
  - ⌞ Over the whole study period as: Exposure duration (in days) \* Actual treatment dosage,
  - ⌞ At each study visits, as: Exposure duration at the visit (in days) \* Actual treatment dosage.

The compliance (%) determined for the following periods:

- Over the whole study period as:

$$100 \left( \frac{\text{Number of patches dispensed} - \text{Number of patches returned}}{\text{Exposure duration in days}} \right)$$

- At each study visit (Day 8, Month 1, 3, 6, 9, 12) as:

$$100 \left( \frac{\text{Nb of patches dispensed}(\text{visit } n - 1) - \text{Nb of patches returned}(\text{visit } n)}{\text{Date of } (\text{visit } n) - \text{Date of } (\text{visit } n - 1)(1)} \right)$$

 Date of current visit – Date of previous visit+1 for Day 8

Compliances exceeding 100% will be set to 100%.

Global compliance of at least 80% over the treatment period is sought.

Additionally, the average daily application duration (in hours) will be summarized descriptively using the subject diary data for the following periods:

- r D1 to D7,
- r D8 to D14,
- r D15 to M3 (D90),
- r M3 (D91) to M6 (D185),
- r M6 (D186) to M9 (D275),
- r M9 (D276) to M12 (end of treatment),
- r D15 to M12

If more than one patch is applied the same day, the daily duration considered is the cumulative application duration of these patches.

In case patches are sequentially applied on the same day: if the end date/time of first patch is not documented, the application date/time of the next patch will be used for imputation.

The percentage of days with no patch application, per subject diary reported data, will also be tabulated, overall and for each of the above periods.

A patch will be considered as “applied” if the date and time of application is documented in the diary.

The start and/or end date/time of patch application used to calculate the duration of patch application are extracted from the diary.

Inconsistencies in the diaries are not queried and only self-evident corrections according to the Data Validation specifications will be made; therefore, inconsistent date/time of patch application or patch removal may remain in the data. In case where calculation of patch application duration leads to a negative value or duration cannot be calculated (missing date or time of removal or invalid dates or times) then:

CCI

CONFIDENTIAL

Project Document Version No. 3.0

Project Document Effective Date: 04-Oct-2017

Page 31 of 79

- The duration of patch application will be considered as ‘unknown’ and not used in the calculation of the average duration of patch application
- For any other calculation based on the number of days with patch application, this day will be considered as a day with application.

These data will be reported as:

- Descriptive statistics for study duration, treatment exposure duration, total dose of protein and compliance (overall and by visit - except for study duration -),
- Number and percent per category of overall exposure (in days, categories are: 1-7, 8-14, 15-30, 31-90, 91-185, 186-275, 276-365, >365), compliance in classes (<80%, ≥80%).

Study duration, treatment exposure and compliance will be summarized for the Safety population in tables that will be produced for each treatment group and overall (except for peanut protein dose that will only be described for the Viaskin Peanut 250 µg arm), globally and by screening ED subgroup.

All data including documentation of treatment interruptions will be listed by treatment group.

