**Figure 2: Schematic Representation of Viaskin® Patch Application on the Back of the Subjects**

To better ensure the safety of the Viaskin® patch at the initiation of treatment, the duration of application of the Viaskin® patch will be progressively increased as follows:

- During the first week (from Day 1 through Day 7), the patches will be applied for 6 hours every day;
- During the second week (from Day 8 through Day 14), the patches will be applied for 12 hours every day;
- From the third week onwards (Day 15), the patches will be applied for the entire 24 hours.

If possible, the subjects should take advantage of their shower/bath time to change the patch. The previous Viaskin® patch should be removed just before the shower/bath, and the new Viaskin® patch should be applied a few minutes after the shower/bath and after drying the skin. Application of the Viaskin® patch at a similar time for each daily application (morning or evening) is recommended. If the subject does not bathe or shower daily or at the same time daily, it is recommended that the zone to which the patch will be applied be cleaned with a moist disposable napkin or tissue and dried prior to application.

A Viaskin® patch must not be re-applied. In case the Viaskin® patch comes off, it should be immediately discarded.

A new patch can be applied the same day to replace the previous patch that came off only if that patch came off within 2 hours after being applied. However, no new patch should be applied the same day if the previous patch came off more than 2 hours after being applied. In that case, a new patch will be applied once 24 hours have passed since the previous patch (the one that came off) was applied. After the Viaskin® patch comes off,

or after removing a Viaskin® patch to apply a new one, it is recommended that the subject's parents/guardians wipes the zone with a moist disposable napkin or a moist disposable tissue and then washes her/his hands to prevent accidental manual transmission of peanut protein.

After the first application of the Viaskin® patch at the study site, all subjects will be observed for 3 hours before being discharged in order to check and grade any reactions under or around the patch.

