### 5.6 Compliance

It is the Investigators' responsibility to ensure that subjects (parents/guardians) are correctly instructed on how to store and administer the study drug. Records of study drug used and intervals between visits will be kept during the study. Drug accountability will be monitored by PAREXEL's site monitor during site monitoring visits and at the completion of the study. Subjects (parents/guardians) will be asked to return their unused study drug (boxes) when they come back for their study visits. All unused study drug (boxes) should be returned at the end of the study to the study drug distributor. The study drug should be dispensed by the Investigator, or by a qualified individual under the Investigator's supervision. An up-to-date treatment inventory/dispensing record must be maintained (see Section 5.5).

At each visit, prior to dispensing the study drug, previously dispensed study drug will be retrieved by the Investigator and compliance assessed. A global compliance of  $\geq 80\%$  over the whole treatment period is sought. Global compliance is defined as the total number of patches applied in the treatment period versus the number of days in that period of time. Compliance at each visit is to be calculated taking into account the total number of patches applied since the last visit versus the number of days in that period of time. Subjects exhibiting poor compliance (below 80%) at any specific time point during the treatment period should be counseled on the importance of good compliance to the study dosing regimen.

Subjects who are persistently non-compliant will be withdrawn from the study.

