#### **7.2.10 Visit 11 ( $\leq 1$ week after Visit 10), End of Treatment Period**

Visit 11 corresponds to the end of the 12-month treatment period. Patch application ends at this visit. The patch worn by the subject when she/he arrives to this visit is removed and there will be no further patches applied beyond Visit 11.

Visit 11 corresponds to the second day of the post-treatment DBPCFC after 12 months of treatment. It takes place within a week following the first day of the post-treatment DBPCFC.

The following assessments will be performed at this visit:

- Physical examination (including a complete skin examination; to take place before DBPCFC; see [Section 6.2.4](#));
- Vital signs (to take place before DBPCFC; see [Section 6.2.3](#));
- PEF (to take place before DBPCFC; see [Section 6.2.6](#));
- Post-treatment DBPCFC (second day) (see [Section 6.1.1](#))
- AEs recording (including volunteered or solicited AEs, AESIs, and recording of AEs/allergies in response to the DBPCFC);
- Concomitant medications (including any medications given to treat allergic symptoms) (see [Section 5.8](#));
- Check for any accidental peanut consumption (see [Section 6.4.4](#));
- Check that the subject diary has been completed accurately and ensure that the subject/parents/guardians is/are comfortable with using the diary;
- Dispense subject diary (re-instruct subjects/parents/guardians on the use, if necessary; see [Section 6.2.7](#));
- Collect the treatment box dispensed at the visit 10 (Month 12 visit), check the unused medication and assess medication compliance;
- Patch adhesion Investigator's assessment: with the patch still applied, the Investigator assesses the adherence of the patch to the skin as well as the occlusion of the patch chamber;
- Check skin reactions of all zones of application and grade the overall severity of the skin reactions (see [Table 6](#), [Section 6.2.8](#));
- Take a photograph of the sites of application of the Viaskin® patch, load it onto the PEPITES website (described in [section 6.2.8](#)) and keep it in the subject's medical records or source documents;
- Schedule Visit 12.

Physical examinations, assessment of vital signs and PEF measurements can be repeated during the DBPCFC as deemed necessary by the Investigator.

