#### 4.3.2 Protocol Deviations

Deviations from the protocol including violations of inclusion/exclusion criteria will be assessed as “minor” or “major” in cooperation with the Sponsor prior to unblinding.

Major protocol deviations (PDV) are defined as those deviations from the protocol likely to have an impact on the perceived efficacy and/or safety of the study treatment. The impact of major PDV on the efficacy and/or safety results will be investigated by assessing the robustness of the study results and conclusions to the choice of analysis population (see [Section 4.4](#)), both including and excluding data potentially affected by major PDV.

Observable PDV data will be entered into PAREXEL’S Clinical Trials Management System (CTMS). Some PDV will be identified via programmed edit checks and listings. The study team and the Sponsor will conduct on-going reviews of the PDV data from the CTMS and the PDV listings and the resulting set of evaluable subjects throughout the study, adjusting the PDV criteria (major/minor PDV) as appropriate.

The evaluable subject sets must be finalized prior to database lock.

PDV will help to define the subjects to be excluded from the PP population.

The two following violation criteria (as Mentioned in [Appendix 1: Major Protocol deviations](#)) have been pre-defined to be excluded subjects from the PP analysis:

- Subjects who do not perform the DBPCFC at 12 months of EPIT treatment,
- Subjects with global treatment compliance below 80%.

Listings will be created to aid the review of data and identification of possible PDV.

The number and percentage of subjects with major PDV will be summarized by type of deviation, overall and by treatment group for all randomized subjects. All PDV data will be listed.

Major PDV and any action to be taken regarding the exclusion of subjects or affected data from specific analyses are specified in [Appendix 1: Major Protocol deviations](#).

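### SAP 4.7 divides whole-study compliance by first-to-last-patch days instead of the protocol's treatment period, so the under-80% per-protocol rule cannot see permanent early stopping

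*SAP*

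**What the plan says.** Protocol 5.6 states: "Global compliance is defined as the total number of patches applied in the treatment period versus the number of days in that period of time". Protocol 7.2.10 fixes the end of that period: "Visit 11 corresponds to the end of the 12-month treatment period". Protocol 8.4 refers compliance back to 5.6 and defines exposure duration separately, as a measure that ignores temporary interruptions.

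SAP 4.7 merges the two. Its whole-study compliance is patches dispensed minus patches returned, divided by the "exposure duration (in days", which for the whole study is "Date of last patch application – Date of first patch application +1". It adds: "Compliances exceeding 100% will be set to 100" per cent. The same section says that the 80% target applies over the treatment period, and its by-visit formula divides by the days between visits. Both of those follow the protocol; only the whole-study formula departs from it. SAP 4.13, which lists changes from the protocol, is silent on this.

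The figure feeds a rule. SAP 4.3.2 names two pre-defined per-protocol exclusions: not performing the Month 12 challenge, and "Subjects with global treatment compliance below 80" per cent. SAP Appendix 1 repeats both.

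**The concern.** With exposure duration as the denominator, the clock stops at the last patch. A child who stops for good is judged only on the days before stopping, however early that was. If the child stays in the study and is challenged at Month 12, neither pre-defined exclusion applies, although the child may have been treated for half the intended period or less.

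What is at stake is how the per-protocol results and the table of compliance below or above 80% are read. Both are meant to describe children who took the treatment over 12 months. The two formulas in SAP 4.7 can also contradict each other for one child: near 0% at Months 9 and 12, yet 100% overall.

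**Working it through.** The plan gives no figure to reproduce, so both written formulas are evaluated directly.

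**Inputs**
- Treatment period T: 365 days, an assumption for 12 months. The range is 358 to 379 days, from the Month 12 window of ±7 days plus up to one week to Visit 11 (365 − 7 = 358; 365 + 7 + 7 = 379).
- Threshold: 80% (SAP 4.3.2, Appendix 1).
- Pattern: patches on a fraction u of days from Day 1 to Day s, none afterwards, and all unused patches returned.

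**Formulas**
- SAP: 100 × (u × s)/s = 100u, capped at 100. The stop day cancels out.
- Protocol: 100 × (u × s)/T.

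**Daily use (u = 1), T = 365**

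| Last patch | SAP 4.7 | Protocol 5.6 |
|---|---|---|
| Day 30 | 100% | 30/365 = 8.2% |
| Day 90 | 100% | 90/365 = 24.7% |
| Day 180 | 100% | 180/365 = 49.3% |
| Day 270 | 100% | 270/365 = 74.0% |

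For the Day 180 case, the protocol figure is 180/358 = 50.3% or 180/379 = 47.5% at the ends of the range.

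**Imperfect use before stopping**
- 90% use to Day 180: SAP 162/180 = 90.0%; protocol 162/365 = 44.4%.
- 80% use to Day 90: SAP 72/90 = 80.0%, kept; protocol 72/365 = 19.7%, excluded.
- 70% use to Day 180: SAP 70%, so excluded under both definitions.

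**Where the definitions disagree.** The SAP keeps the child when u is at least 0.8. The protocol excludes when u × s/T is below 0.8, that is, when s is below 0.8T/u. For a daily user that is 0.8 × 365 = Day 292, or 365 − 292 = 73 days before the end (0.8 × 358 = 286.4 and 0.8 × 379 = 303.2 at the ends of the range). At 90% use the limit moves later, to 292/0.9 = Day 324. So stopping more than about 73 days early is enough for disagreement in anyone with at least 80% prior use, and less is enough for those who had already missed days.

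**What the SAP formula does capture.** Gaps followed by a later patch are counted. Daily use to Day 180 and then a single patch on Day 365 gives 181/365 = 49.6%. Only a final stop is invisible.

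**The case against.** The strongest reply is that few children can fall into this gap. Protocol 4.3.4 sends anyone withdrawn from study drug to an Early Termination Visit, which has no food challenge (7.2.12), and the missing challenge then excludes the child. Protocol 5.6 has persistently non-compliant subjects withdrawn. What remains is children who stop for good, are not withdrawn, and still attend Month 12. For them, SAP Appendix 1 leaves the deviation categories to be finalised at blinded review and lists meeting withdrawal criteria without being withdrawn as a possible ground for exclusion. By-visit compliance and the diary tabulations would make the stop visible. All of this stands and limits the reach of the point. It does not repair the 80% rule, because none of these routes is a numerical rule that replaces it.

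Three stronger readings are tempting, and the documents do not support them.
- *The trial's conclusion is at risk.* SAP 4.8.2 decides success on ITT with missing counted as failure, every step in SAP Table 2 uses ITT, and SAP 4.4.4 calls the per-protocol analyses sensitivity analyses, although protocol 8.1.3.4 calls them confirmatory. Under-treated active children kept in the per-protocol set would most plausibly dilute the effect there.
- *The active arm is affected more.* Protocol 1.1.1.2.3 reports local reactions in over 90% of active and 50% of placebo subjects in the Phase IIb study, but withdrawal for them in only 2 of 221. Section 1.1.1.2.6 reports no withdrawals of children due to adverse events. More reactions do not establish more stopping.
- *The numerator also departs from the protocol because replacement patches count.* Protocol 5.2 allows this ("A new patch can be applied the same day to replace the previous patch that came off", within 2 hours of application), and 5.6 itself counts patches applied. Counting days with a patch would be a new definition. Unreturned patches do count as used under the SAP proxy, and the cap can hide the excess, but the documents give no size for this.

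**Conclusion.** The inconsistency is real, unlisted and confined to one denominator. For a child with at least 80% use up to a permanent stop more than about 73 days before the end of a 365-day period, who completes the Month 12 challenge, SAP 4.7 returns 80% to 100% where protocol 5.6 returns less than 80%. In the Day 180 example the gap is 100% against 49%. The stated rule then fails to exclude the child, although judgement at blinded review still may.

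This rests on a 12-month period taken as 365 days, return of unused patches, and a child who is never formally withdrawn. How many such children there would be is unknown. The consequence is limited to the per-protocol sensitivity analyses and the compliance tables. It is worth correcting because the correction is nearly free, not because the primary result depends on it.

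**What to change.** In SAP 4.7, for subjects who complete the Month 12 challenge, set the whole-study compliance denominator to the days from first patch to the end of the treatment period (Visit 11). This restores the protocol 5.6 basis: "total number of patches applied in the treatment period versus the number of days in that period of time". Exposure duration can remain as a separate summary, as protocol 8.4 has it. Subjects without the challenge already leave the per-protocol set, so their end date matters only for the compliance tables. If the sponsor prefers the present formula, SAP 4.13 should list and justify it.

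The cost is one formula, using dates already collected, and it should be settled before unblinding. The downside is that a few more subjects may leave the per-protocol set. The change does not address unreturned patches.
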